4.2. Inclusion Criteria

For inclusion in the study, a patient must meet all general inclusion criteria, as shown below: **General Inclusion Criteria:**

- 1. Patient is at least 18 years old at informed consent
- 2. Patient is willing and capable of complying with all study protocol requirements, including specified follow-up period and can be contacted by telephone.
- 3. Patient is willing to provide written informed consent prior to enrollment in study.
- 4. Patient has no childbearing potential, or is a non-lactating female of childbearing potential practicing an acceptable method of birth control with a negative pregnancy test within 10 days of study procedure.
- 5. Patient is either:
 - Symptomatic with carotid stenosis ≥50% as determined by angiography using NASCET methodology¹³. Symptomatic is defined as amaurosis fugax ipsilateral to the carotid lesion; TIA or non-disabling stroke within 180 days of the procedure within the hemisphere supplied by the target vessel; or
 - Asymptomatic with carotid stenosis ≥80% as determined by angiography using NASCET methodology.
- 6. Patient has a target lesion located at the carotid bifurcation and/or proximal ICA.
- 7. Patient has a single de novo or restenotic (post CEA) target lesion that can be covered by a single 40mm stent.
- 8. Patient has a stent landing zone diameter between 3.7 mm and 9.0 mm

High Risk Inclusion Criteria:

For inclusion in the study, a patient must qualify in **at least one** High-Risk condition, as shown below:

Anatomic Conditions

- 1. Patient has surgically inaccessible lesions at or above the level of C2 or below the clavicle.
- 2. Patient is status/post radical head or neck surgery or radiation therapy.
- 3. Patient has spinal immobility of the neck.
- 4. Patient has the presence of tracheostomy stoma.
- 5. Patient has laryngeal palsy or laryngectomy.
- 6. Patient has contralateral laryngeal nerve paralysis.
- 7. Patient has restenosis after a previous CEA.

Co-morbid Conditions

[figure not shown]
- 1. Patient is \geq 75 years of age at time of enrollment.
- 2. Patient has NYHA Class III or IV congestive heart failure (CHF).
- 3. Patient has chronic obstructive pulmonary disease (COPD) with FEV <30%.
- 4. Patient has a left ventricular ejection fraction (LVEF) <30%.
- 5. Patient has documented uncontrolled diabetes.
- 6. Patient has unstable angina with ECG changes.
- 7. Patient has had a recent myocardial infarction (≥72 hours, <30 days).

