5.14. Subject Study Completion

A subject has completed the study when he/she has completed the 3-year follow-up evaluations. Any subject that does not complete these requirements due to voluntary withdrawal, physician withdrawal, death, or any other reason will be considered as an early withdrawal. In the event of a Technical Failure (no GORE[®] Carotid Stent implanted), the subject will be followed through the 30-day visit and will be considered to have completed the study.

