#### Figure 2. Study Procedures and Evaluation Schema

#### 3.2 Study Interval Windows

Subjects with successful test device implant will return for follow-up at 30 days, 6 months, 1, 2 and 3 years. Subjects considered Technical Failures (test device attempted but not implanted) are only required to complete a 30-day follow-up and will have then completed the study. All intervals are calculated from the index procedure. The 6-Month visit target is 180 days. The yearly visits are calculated on a calendar year from index procedure.

30 Days	6 Months	1 Year	2 Years	3 Years
30±7 days	180±14 days	365±30 days	730±45 days	1,095±45 days

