**Target Lesion Revascularization (TLR):** any clinically-driven revascularization procedure of the original treatment site, including angioplasty, stenting, endarterectomy, or thrombolysis, performed to open or increase the luminal diameter inside or within 5 mm of the previously treated lesion. This will be calculated using Kaplan-Meier (K-M) survival analysis. Events will be subjects who experience TLR as reported on the Reintervention CRF. Censored observations will be subjects free of TLR. K-M estimates corresponding to the study follow-up intervals will be reported, as well as a graph of the entire survival distribution.

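### Kaplan-Meier for TLR, with deaths censored by implication, estimates a net probability and somewhat overstates the proportion of subjects who actually have a TLR

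*SAP*

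**What the plan says.** SAP 4.4 sets out the TLR analysis in a few sentences. On the estimator: "This will be calculated using Kaplan-Meier (K-M) survival analysis". On events: "Events will be subjects who experience TLR as reported on the Reintervention CRF". On censoring: "Censored observations will be subjects free of TLR". On output: "K-M estimates corresponding to the study follow-up intervals will be reported, as well as a graph of the entire survival distribution". The section does not mention death, competing events or the date at which a subject is censored.

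Follow-up is long for implanted subjects. SAP 3.2 states: "Subjects with successful test device implant will return for follow-up at 30 days, 6 months, 1, 2 and 3 years". Technical failures, by contrast, "are only required to complete a 30-day follow-up and will have then completed the study".

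Protocol 5.14 puts death in the same completion category as other reasons for leaving: a subject who does not finish "due to voluntary withdrawal, physician withdrawal, death, or any other reason will be considered as an early withdrawal". That sentence is about study status and is not an analysis rule, but it is the nearest the documents come to saying how a death ends a subject's record.

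SAP 4.4 also makes all secondary endpoints descriptive, with no hypothesis tests.

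**The concern.** A subject who withdraws alive can still have a revascularization that the study does not see. A subject who has died cannot. Kaplan-Meier treats both in the same way: each leaves the risk set and is assumed to have the same later TLR risk as those who remain. When deaths are censored, 1-KM answers what the TLR probability would be if nobody died. It does not answer what proportion of treated subjects will have a TLR.

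The two quantities move apart as deaths accumulate. Protocol 4.2 requires at least one high-risk condition, and the list includes advanced heart failure, severely reduced ejection fraction, severe COPD and recent myocardial infarction. Protocol 4.3 excludes a life expectancy under one year, which does little to limit deaths in years 2 and 3. At stake is how the 1-, 2- and 3-year TLR figures are read, and whether they can fairly be compared with series that have different mortality.

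**Working it through.** **Is death censored?** SAP 4.4 has two states: TLR (event) and free of TLR (censored). A subject who dies without a TLR falls in the second. This is an inference, but no other rule is given.

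**Is there a figure to reproduce?** No. The readable text gives no expected TLR rate, no mortality rate and no precision target for TLR. All rates below are assumptions.

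**Inputs.**
- Enrolled subjects: 312 (Protocol 3.1, SAP 2.4).
- Horizon: 3 years (SAP 3.2).
- Net 3-year TLR: assumed 2% to 10%.
- 3-year mortality: assumed 5% to 30%.
- Constant and independent hazards: assumed.

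**Formulas.** With hT the TLR hazard and hD the death hazard per year:
- hT = -ln(1 - net TLR)/3 and hD = -ln(1 - mortality)/3
- 1-KM(t) = 1 - exp(-hT·t)
- Cumulative incidence: CIF(t) = hT/(hT + hD) × [1 - exp(-(hT + hD)·t)]

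**Worked example 1: net TLR 5%, mortality 20%, t = 3.** 3hT = -ln 0.95 = 0.0513 and 3hD = -ln 0.80 = 0.2231. CIF = 0.0513/0.2744 × (1 - 0.95 × 0.80) = 0.1869 × 0.24 = 4.49%. 1-KM is 5.00%, so the excess is 0.51 points.

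**Worked example 2: net TLR 8%, mortality 30%, t = 3.** CIF = 0.0834/0.4401 × (1 - 0.92 × 0.70) = 0.1895 × 0.356 = 6.7%, against 8.0%.

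**Range at 3 years.** The standard error is sqrt[p(1-p)/312], with p the 1-KM value.

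| Net TLR | Mortality | 1-KM | CIF | Excess (points) | Ratio | Approx. SE (points) |
|---|---|---|---|---|---|---|
| 2% | 5% | 2.00% | 1.95% | 0.05 | 1.026 | 0.79 |
| 3% | 10% | 3.00% | 2.85% | 0.15 | 1.053 | 0.97 |
| 5% | 20% | 5.00% | 4.49% | 0.51 | 1.115 | 1.23 |
| 5% | 30% | 5.00% | 4.21% | 0.79 | 1.187 | 1.23 |
| 10% | 5% | 10.00% | 9.75% | 0.25 | 1.025 | 1.70 |
| 10% | 30% | 10.00% | 8.44% | 1.56 | 1.185 | 1.70 |

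Over the whole grid the relative excess runs from about 2.5% to 19%.

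**Range at 1 year.** The same hazards give an excess of 0.01 to 0.20 points. The largest is 3.45% against 3.25%, with net 3-year TLR of 10% and mortality of 30%.

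**Simulation check.** In 4,000 simulated trials of 312 subjects per scenario, the mean excess of 1-KM over the Aalen-Johansen estimate at 3 years was 0.15 points (TLR 3%, mortality 10%), 0.52 points (5%, 20%) and 1.57 points (10%, 30%). In every simulated trial 1-KM was at or above Aalen-Johansen.

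**The case against.** The strongest reply is that Kaplan-Meier is not an error here. If censoring is independent, it validly estimates the net probability of TLR, and for a stent the risk of revascularization among patients still alive is a reasonable measure of durability. The SAP never says that the figure is the share of subjects who will have a TLR. This stands: the excess exists only when the figure is read as that share. What remains is that the SAP does not say which quantity it means, and a reader of a reported TLR rate will naturally take it as the share.

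Several stronger readings are tempting, and the documents do not support them:

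- **That the SAP states that deaths are censored.** It does not; this follows from the two-state rule.
- **That the cohort is elderly by design.** The minimum age is 18, age 75 or over is one of several alternative criteria in Protocol 4.2, and a patient can qualify on anatomy alone. High surgical risk is the accurate description.
- **That mortality is known to be high.** No rate is given, and Protocol 4.3 removes some patients with a poor prognosis.
- **That the 1-year figures are materially distorted.** The 1-year excess is at most about 0.2 points under the assumed rates, and Protocol 3.1 ties the PMA submission to completion of 1-year follow-up.

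It is also fair to say that the excess is smaller than one standard error across the assumed range. It is systematic all the same: it always runs in one direction and grows with follow-up and mortality.

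**Conclusion.** The point holds as an improvement to estimation and labelling. Read literally, SAP 4.4 censors deaths without TLR, so 1-KM is a net probability and lies somewhat above the proportion of subjects who have a TLR. If the curve is shown as freedom from TLR, that freedom is too low by the same amount.

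The size rests wholly on assumed rates and constant hazards. It is about 0.05 to 1.6 percentage points at 3 years and much less at 1 year.

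A reader might infer that the trial's conclusions are at risk. They are not. TLR has no hypothesis, margin or performance goal, the primary endpoint is analysed as a binomial proportion (SAP 4.3), and the excess makes the device look slightly worse.

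**What to change.** In SAP 4.4, treat death without TLR as a competing event. Report the cumulative incidence of TLR (Aalen-Johansen) with confidence limits at each follow-up interval. Keep the Kaplan-Meier curve as a supporting display, labelled as a net probability, so that comparison with other series remains possible. State the censoring date for subjects who are alive and free of TLR.

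The cost is a sentence or two in the SAP and a standard software option. No new data are needed: Protocol 5.13 and 9.1.4 already provide for recording deaths, and 5.13 asks for vital status in subjects who refuse to return. The small downside is two curves to explain.

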#### 4.5 Adverse Events

All site-reported AEs will be MedDRA coded and grouped by MedDRA System/Organ Class (SOC) and by MedDRA Preferred Term within SOC. AEs will also be grouped by seriousness (SAE vs. nonserious AE), primary relationship (stent, EPD, procedure, medication, disease, not related, and unknown) and timing of onset (procedure, pre- and post-discharge). AEs will be summarized as rates given by subject-based binomial proportions. The numerator will be the count of subjects who experienced one or more episodes of the AE of interest in the time period of interest. The denominator will be the count of subjects free of the AE of interest through the time period of interest and with sufficient clinical follow-up for the time period of interest, plus the count of subjects in the numerator. Unless otherwise specified for a particular endpoint measure, all enrolled subjects in the analysis set of interest will be considered evaluable and will contribute to the denominator.

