#### 4.3 **Primary Endpoint**

The primary endpoint of 1-year MAE will be calculated as a subject-based binomial proportion. The numerator will be the count of subjects who experience death, any stroke, or MI through 30 days post-index procedure, or ipsilateral stroke through one year (365 days) post-index procedure. The denominator will be the count of subjects free of MAE and with clinical follow-up of at least 335 days post-index procedure, plus the count of subjects in the numerator. Only MAE adjudicated by the CEC will be used in this analysis. Acceptable clinical follow-up includes the Subject Evaluation CRF, duplex ultrasound, modified Rankin scale, and NIHSS.

A one-sided 95.1% upper confidence bound will be calculated (using the standard error based on  $H_0$ ) and compared to the prespecified performance goal. If this bound is less than the performance goal, then the primary endpoint is met and the test device will have demonstrated acceptable performance. The *P* value for the corresponding one-sided normal

approximation to the binomial test will be reported. The primary hypothesis test will use  $\alpha$ =0.049 to ensure an overall Type-1 error rate  $\leq$ 0.05.

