**30-Day Major Adverse Events:** Composite of death, any stroke, or myocardial infarction through 30 days post-index procedure. It will be calculated as a subject-based binomial proportion. The numerator will be the count of subjects who experience CEC-adjudicated MAE through 30 days post-index procedure. The denominator will be the count of subjects free of MAE through 30 days post-index procedure and with clinical follow-up of at least 23 days post-index procedure, plus the count of subjects in the numerator.

**In-stent Restenosis:** Measured as percent stenosis at follow-up evaluation within the stented lesion or within 5 mm proximal or distal to the stent. Additionally will assess percent of subjects with stenosis  $\geq$ 50% by ultrasound and  $\geq$ 80% by angiographic evaluation.

The text above is taken verbatim from the clinical protocol. There are three separate endpoint measures implied by this description, defined below:

**In-stent Percent Diameter Stenosis:** calculated as a subject-based categorical frequency distribution of "In Stent Stenosis Category" as reported on the Carotid Artery Duplex Scan CRF among subjects with a valid, nonmissing value for this item.

The stenosis categories are the following:

- Patent
- 50-79%
- >70%
- 80-99%
- Occluded

**In-stent Restenosis By Ultrasound:** calculated as a subject-based binomial proportion. The numerator will be the count of subjects with stenosis ≥50% by ultrasound (indicated as any valid, nonmissing stenosis category other than "Patent") as reported on the Carotid Artery Duplex Scan CRF. The denominator will be the count of subjects with a valid, nonmissing value for this item.

**In-stent Restenosis By Angiography:** calculated as a subject-based binomial proportion. Restenosis failures will be indicated by an angiography core lab-adjudicated stenosis of ≥80% as reported on the Angio Core Lab Adjudication CRF. Not all subjects will have a follow-up angiography performed, only those whose ultrasound-determined stenosis and/or clinical symptoms provokes an angiography by the investigator. The denominator will be the count of subjects with a valid, nonmissing value for ultrasound-determined stenosis.

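### SAP 4.5 gives two adverse event denominators that disagree for event-free subjects with incomplete follow-up, and its default understates AE rates in windows well past discharge

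*SAP*

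**What the plan says.** SAP 4.5 (Adverse Events) summarises AEs as subject-based proportions. The numerator is "the count of subjects who experienced one or more episodes of the AE of interest in the time period of interest". The denominator is then given in two consecutive sentences:

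- The first takes event-free subjects "with sufficient clinical follow-up for the time period of interest, plus the count of subjects in the numerator".
- The second begins "Unless otherwise specified for a particular endpoint measure" and continues that "all enrolled subjects in the analysis set of interest will be considered evaluable and will contribute to the denominator".

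Section 4.5 does not say how much follow-up is enough. Two measures elsewhere in the SAP do have their own minimum. The primary endpoint (4.3) uses event-free subjects "with clinical follow-up of at least 335 days post-index procedure, plus the count of subjects in the numerator", and the 30-day MAE (4.4) uses event-free subjects "with clinical follow-up of at least 23 days post-index procedure, plus the count of subjects in the numerator".

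AEs are grouped by "timing of onset (procedure, pre- and post-discharge", and the last of these categories has no stated end. Protocol 9.1.3 has AEs reported from enrollment until the subject completes or leaves the study, which is up to three years for implanted subjects. SAP 3.2 says that technical failures "are only required to complete a 30-day follow-up and will have then completed the study". SAP 4.1.1 limits the intent-to-treat (ITT) AE analysis to 30 days for that reason. SAP 4.2.2 adds a staged report on the first 50 enrolled subjects, with safety results at procedure, 30 days and 6 months.

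**The concern.** Take an event-free subject who withdraws or is lost partway through a reporting window. The first sentence leaves that subject out of the denominator and the second puts the subject in. For the tables by organ class, preferred term, seriousness, relationship and timing, no endpoint-specific minimum settles which sentence governs. Two programmers could follow the SAP in good faith and produce different rates from the same data.

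The default also has a direction. A subject who is no longer observed adds one to the denominator and cannot add to the numerator, so unobserved time is read as event-free time. The study has no concurrent control (SAP 2.2.2), so AE rates are read as absolute values and no second arm carries the same dilution. Procedure and pre-discharge rates are hardly touched. The rates exposed are those after discharge, those over longer windows, and those in the 6-month staged report.

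**Working it through.** The plan states no AE rate, AE denominator count or readable loss rate, so there is no figure to reproduce. The check compares the two rules on the same hypothetical data.

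**Inputs**

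- N = 312 enrolled (Protocol 3.1; SAP 2.4).
- True AE risk over the window, p = 10%. This is an assumption.
- Loss over the window, d = 5%, 10% or 20%. This is an assumption.
- Loss means withdrawal or loss to follow-up, not death.

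**Case 1: all loss occurs before the window opens.** Observed events are p × N × (1 − d).

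- Follow-up rule: pN(1 − d) / N(1 − d) = p, which is 10.0% at every d.
- Default: pN(1 − d) / N = p(1 − d), which is 9.5%, 9.0% and 8.0% at d = 5%, 10% and 20%.

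**Case 2: loss is spread over the window.** Assume a constant event hazard h = −ln(1 − p) and an independent constant loss hazard g = −ln(1 − d).

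- Observed events: E = N × h/(h + g) × (1 − e^−(h+g)).
- Event-free with full follow-up: C = N × e^−(h+g) = N(1 − p)(1 − d).
- Follow-up rule: E/(E + C). Default: E/N.

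At d = 10%, h = g = 0.10536. Then E = 312 × 0.5 × (1 − 0.81) = 29.64 and C = 312 × 0.81 = 252.72. The default gives 29.64/312 = 9.5%. The follow-up rule gives 29.64/282.36 = 10.5%. The other rows follow in the same way:

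| Loss d | E | C | Lost, event-free when last seen | Default E/N | Follow-up rule E/(E + C) |
|---|---|---|---|---|---|
| 5% | 30.43 | 266.76 | 14.81 | 9.8% | 10.2% |
| 10% | 29.64 | 252.72 | 29.64 | 9.5% | 10.5% |
| 20% | 28.02 | 224.64 | 59.34 | 9.0% | 11.1% |

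The follow-up rule overshoots because it keeps an early leaver who had the event before leaving and drops one who did not.

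**Staged 6-month report.** Enrollment means that the device was attempted (SAP 2.3), so the first 50 enrolled can include technical failures. They have no required follow-up after the 30-day visit. If the default is applied to these 50, each technical failure is 1/50 = 2% of the denominator and is unobserved for most of the six months. Events in the first 30 days are still captured, so the relative understatement is at most 2% per technical failure.

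**The case against.** The strongest reply is that the second sentence does not contradict the first but completes it. It can be read as a default definition of who is evaluable, displaced where a measure sets its own minimum, as the 335-day and 23-day rules do. That reading is fair and removes the contradiction. It also makes the all-enrolled denominator govern every other AE table, so the understatement stays. If the first sentence governs instead, the required follow-up is undefined.

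Several stronger claims that a reader might infer are not supported:

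- **That technical failures dilute all later AE rates.** SAP 4.1.1 stops the ITT AE analysis at 30 days, and the per-protocol set (4.1.2) requires an implanted device. If those sets are respected, technical failures matter after day 30 only in the staged report, where 4.2.2 names the first 50 enrolled and no analysis set. In the per-protocol set the dilution comes from withdrawal and loss.
- **That deaths bias the default.** A subject who dies without the AE cannot have it later. Keeping that subject in the denominator is a legitimate cumulative incidence.
- **That the study's success decision is affected.** The primary endpoint and 30-day MAE have their own denominators. The AE summaries are descriptive, and no hypothesis test changes.

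Two further points stand. The SAP specifies no 1-, 2- or 3-year AE table; the one later safety time point it names is the 6-month staged report. At low loss the gap is small.

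**Conclusion.** The point holds within limits. SAP 4.5 gives two denominators that differ for event-free subjects with incomplete follow-up. On any reading that lets the default govern, withdrawn and lost subjects count as event-free for unobserved time, and AE rates in windows well past discharge come out too low. The direction needs no assumption about the amount of loss, but the size does. For a true 10% risk with loss spread over the window, the two rules are about 0.4 percentage points apart at 5% loss (10.2 − 9.8), 1.0 at 10% (10.5 − 9.5) and 2.1 at 20% (11.1 − 9.0), one below the truth and one above. If all loss comes before the window, the default alone is off, by 0.5, 1.0 and 2.0 points. These figures assume independent loss and, in the spread case, constant hazards. The documents contain no readable loss rate to choose among them.

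It would be wrong to conclude that the follow-up rule is simply the correct one, because it errs upward when loss is spread over the window. The matter should be settled before the AE tables are programmed. It does not touch the primary test.

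**What to change.** Replace the two sentences in SAP 4.5 with one rule per window:

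- **Procedure and pre-discharge AEs:** all enrolled subjects in the analysis set. Restrict the all-enrolled sentence to these.
- **AEs through 30 days:** the follow-up rule, with the 23-day minimum that SAP 4.4 already uses for the 30-day MAE. Say explicitly that a subject who dies before day 23 without the AE stays in the denominator. There is little time for loss to accumulate, so the upward error should be small.
- **AEs beyond 30 days, including the 6-month staged report:** time-to-first-event cumulative incidence with numbers at risk. Censor at last contact, which for technical failures is their exit at the 30-day visit. Treat death without the AE as a competing event; censoring deaths in a Kaplan-Meier complement would overstate AE risk.

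SAP 4.2.2 should also name the analysis set for the 6-month results. SAP 4.4 already uses Kaplan-Meier for target lesion revascularization, so time-to-event reporting is not new to the plan. The cost is a wording change and minor extra programming. Some later AE rates will look slightly less favourable than under the default.
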